9 ENDPOINTS

Endpoints are reached at 12 months. Selected measurements will also be obtained at 10 days, 30 days, 6 months, 24 months, and 36 months.

9.1 CO-PRIMARY ENDPOINTS & SUCCESS CRITERIA

Table 1 provides a list of the test method, subject success criteria, and study success criteria for the co-primary endpoints. The co-primary endpoints are reached at 12 months.

Table 1 Co-Primary Endpoints & Success Criteria

Co-Primary Endpoint	Test Method	Subject Success Criteria ^{Note 1}	Study Success Criteria ^{Note 2}
Reduction in Menstrual Blood Loss (MBL) at 12 months	Pictorial blood loss assessment chart (PBAC), Appendix F. This is a validated measure of MBL ⁹ . Scoring instructions are included in Appendix G.	≥ 50% reduction in PBAC score, and a final PBAC score < 250	LCL of the percentage of subject success ≥ 45%
Rate of surgical re-intervention for HMB due to treatment failure at 12 months	Surgical re-intervention for HMB due to treatment failure	No surgical re-intervention for HMB due to treatment failure at 12 months	LCL of the percentage of subject success ≥ 75%

Table Notes

- 1) Subject success is calculated separately for the two co-primary endpoints, such that it is possible for a subject to be considered a success for one co-primary endpoint and not for the other.
- 2) Study success is achieved if both of the study success criteria are met.

⁹ Janssen C, Scholten P, Heintz P. A simple visual assessment technique to discriminate between menorrhagia and normal menstrual blood loss. *Obstet & Gynec.* 1995;85:977-982.

9.2 SECONDARY ENDPOINTS

Table 2 provides a list of the secondary endpoints in the study and the method of measurement for each. The secondary endpoints are reached at 12 months.

Table 2 Secondary Endpoints

Secondary Endpoint	Test Method
Safety - Adverse Device Effects	Procedure safety will be assessed by recording all adverse device effects that occur during or subsequent to treatment on the day of the procedure. Longer-term safety will be assessed by recording at each follow-up visit any untoward medical occurrence since baseline. Each adverse device effect will be assessed for severity.
Reduction in total and perfused fibroid volumes	Change in total and perfused volume of clinically relevant fibroids will be determined by comparing contrast-enhanced MRI at baseline and at 12 months. All MRI's will be forwarded to a central reader (core lab).
Change in the symptom severity and quality of life subscales of the Uterine Fibroid Symptom and Quality of Life (UFS-QOL) Questionnaire	The Symptom Severity Score (SSS) and Health-Related Quality of Life Score (HRQL) are calculated from a subset of the Uterine Fibroid Symptom and Quality of Life (UFS-QOL) questionnaire, a validated and fibroid-specific assessment tool. ¹⁰ The questionnaire and the SSS component have been used in several studies of subjects with fibroids. A copy of the UFS-QOL questionnaire is included as Appendix B.
Time to return to normal daily activity (days)	Subjects will be given a Treatment Recovery Questionnaire at discharge and asked to complete questions daily regarding return to normal activities for the first two weeks post-procedure. A copy of the questionnaire is included as Appendix C.
Overall subject treatment outcome using the Overall Treatment Effect Scale (OTE)	Subject-perceived overall treatment effect (OTE) will be assessed using the OTE Scale. ¹¹ Subjects will be asked to indicate whether their uterine fibroid symptoms have improved, remained the same, or worsened. If the subject indicates that her symptoms have improved, she will be asked to rate the degree of improvement on a 7-point scale from "almost the same, hardly better at all" (1) to "a very great deal better" (7). If the subject indicates that her symptoms worsened, she will be asked to rate the degree of worsening on a 7-point scale from "almost the same, hardly worse at all" (-1) to "A very great deal worse" (-7). OTE is assessed as part of the Subject Satisfaction Questionnaire included as Appendix I.

¹⁰ Spies JB, Coyne K, Guaou G, Boyle D, Skyrnarz-Murphy K, Gonzalves SM. The UFS-QOL, A new disease-specific symptom and health-related quality of life questionnaire for leiomyomata. *Obstet Gynecol.* Feb 2002;99(2):290-300.

¹¹ Jaeschke R, Singer J, Guyatt GH. Measurement of health status. Ascertaining the minimal clinically important difference. *Control Clin Trials.* 1989;10(4):407-415.

Secondary Endpoint	Test Method
Subject Satisfaction	Subjects will be asked to rate their level of satisfaction with the treatment and whether they would recommend the procedure to a friend with the same health problems. The Subject Satisfaction Questionnaire is included as Appendix I.
Change in general health outcome	EuroQOL EQ-5D. The EQ-5D is a standardized instrument for use as a measure of health outcome. Applicable to a wide range of health conditions and treatments, it provides a simple descriptive profile and a single index value for health status. A copy of the US version of the questionnaire is included as Appendix A. ¹²
Subject pain and tolerance of procedure	Prior to discharge, subjects will be asked to rate their tolerance of the procedure and rate their experience of pain using a pain VAS.
Mean length of stay (LOS)	Length of stay (in hours) will be assessed by recording the duration from the start of the procedure to discharge. If recovery time is not longer than expected and study center scheduling prevents same-day discharge, LOS will be calculated based on the time at which discharge would otherwise have occurred as documented by the Investigator in the CRF.
Occurrence of Pregnancy and Pregnancy Outcome	Subjects will be asked at each study visit about the possible occurrence of pregnancy. If a pregnancy has occurred, information regarding pregnancy outcome will be recorded from subject self-report and from medical records if available at the study site.
Work Productivity and Activity Impairment	WPAI:SHP. The WPAI is a standardized instrument for use in assessing productivity and activity impairment for use in health economics outcomes research. ¹³ The WPAI:SHP is a version of the WPAI as adapted to address a specific health problem. The questionnaire is adjusted from its validated 7-day time frame to a 28-day time frame to capture the impact of uterine fibroids over a full menstrual cycle. A copy of the US English version of the questionnaire is included as Appendix K

10.1 Selection Criteria

Please refer to Section 4L on page 11.

10.2 Subject Identification

Each subject will be assigned a unique subject identification number at the time of signing the informed consent. This subject identification number will be used during screening and retained throughout the study if the subject is enrolled. Investigational sites will keep a confidential log that notes the subject's name and corresponding subject identification number. All case report forms will be tracked, evaluated, and stored using only the subject ID number and initials. No personal identifying information will be included on the case report forms.

"Protected Health Information" will be maintained in compliance with the Health Insurance Portability and Accountability Act of 1996 (HIPAA) Privacy rule.

The informed consent form will notify subjects that study monitors, auditors, and representatives of government agencies will have access to personal identifying information to ensure that data reported on the case report forms corresponds to the person who signed the consent form and the information contained in the source documentation.

10.3 Informed Consent Process

- A. The Investigator will obtain written informed consent from the subject using the IRB/EC-approved consent form prior to initiation of any study-specific assessments or procedures that are not part of routine care. The consent form shall be provided in a language understandable to the subject. Consent of the subject is documented by the dated signatures of the subject, witnesses if applicable, the person conducting the consent discussion, and the Investigator if required by the governing IRB.
- B. In some cases, local regulations require one or two impartial witnesses. In these cases, after the written informed consent form and any other written information to be provided to subjects is provided and explained in the subject's own language, and after the subject has orally consented to the subject's participation in the trial and, if capable of doing so, has signed and personally dated the informed consent form, the witness should sign and personally date the consent form. By signing the consent form, the witness attests that the information in the consent form and any other written information was accurately explained to, and apparently understood by, the subject, and that informed consent was freely given by the subject.

- C. Potential subjects will be given adequate time to review the consent form, ask questions, and consider their options before being asked to sign the form. Informed consent shall be obtained under circumstances that are intended to prevent coercion or undue influence. The information that is given to the subject shall be in language understandable to the subject. The subject will not be led to believe that they are waiving their rights as a subject or the liability of the sponsor or Investigator.
- D. Subjects will be informed that the sponsor and regulatory authorities will have access to personally identifying information for the purposes of monitoring data against source documentation. However, all data stored and presented by the sponsor will be in anonymous form.
- E. One original, signed and dated informed consent will be retained in the subject's study records and a copy (or second original) provided to the subject. A third copy of the consent form, or a progress note documenting the consenting process and date will be added to the patient medical chart in accordance with investigational site policy.
- F. Any modification to the study sample informed consent form made by the Investigational Site must be approved by the sponsor and the IRB/EC before use. Each Investigational Site will provide the sponsor with a copy of the IRB/EC-approved consent forms.
- G. Informed consent completion will be monitored regularly by the sponsor or sponsor representatives.

10.4 Moment of Enrollment

Subjects will be considered "enrolled" in the study once the approved consent form is signed and compliance with all inclusion and exclusion criteria has been verified and documented. At that point, the subject will enter the treatment phase of the study.

10.5 Subject Adherence

- A. The Investigator should instruct the subject regarding the importance of complying with the data collection and follow-up visit requirements. Poor subject adherence may result in the sponsor discontinuing the subject from the study.
- B. Subjects will be asked at each follow-up visit if they have adhered to study instructions regarding continuous use of the same means for birth control.

10.6 Subject Discontinuation or Withdrawal

- A. Subjects may be involuntarily removed from the study for failure to adhere to the protocol, failure to attend follow-up visits, or due to safety reasons. In such cases, the Investigator shall arrange for an exit visit and complete a study exit case report form for the subject.
- B. Subjects may voluntarily withdraw from the study at any time without reason. The Investigator shall make an effort to obtain an exit visit but cannot insist on the visit if the subject does not wish to come in. The Investigator shall complete a study exit case report form with as much information as is available at the time of withdrawal.
- C. In cases of early termination, as many of the month 12 study procedures should be performed as possible at the time of withdrawal. All information relative to the withdrawal must be fully documented in the subject chart.
- D. If the subject requires removal from the study due to medical reasons (i.e. adverse event) or reasons related to the procedure, the site staff should contact the Gynesonics Medical Director. Adverse device effects that are ongoing at the time of withdrawal will be reported and followed up to 6 weeks following the study treatment or until the adverse device effect resolves or is considered stable, whichever comes last, unless the subject has withdrawn consent for any such follow-up. In such cases, the final follow-up can be either a telephone contact or an office visit.
- E. A subject will be withdrawn from the study if, subsequent to enrollment, she is diagnosed with any condition that could affect menstrual bleeding volume, or if she becomes pregnant at any time following Sonata treatment. In the case of pregnancy, the Investigator and study coordinator should make every attempt to obtain basic pregnancy outcome information and complete the applicable case report form.
- F. A subject may be withdrawn after enrollment and before receiving the study treatment if, at the Investigator's discretion, she has developed a general health condition that would increase risks from study treatment

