13.1 Potential Risks

Ultrasound and radiofrequency electrosurgery are both well-established technologies. To qualify for participation in this study, investigators will have performed open and minimally invasive gynecologic procedures involving ultrasound, laparoscopic and/or hysteroscopic surgery and electrosurgery, and have extensive experience to safely manage both anticipated and unanticipated operative and investigational occurrences.

Intrauterine sonography-guided RF ablation does not require the level of uterine distention required for hysteroscopic surgery. The volume of fluid instillation is small, pressure within the endometrial cavity would not be greater than mean arterial pressure, and no large venous sinuses are exposed that would promote fluid intravasation. Therefore, the risks of fluid overload (hyponatremia) and pulmonary/cerebral edema associated with hysteroscopic myomectomy do not apply to the Sonata procedure.

Risks associated with the use of the Sonata System are expected to be similar to other complications associated with hysteroscopic fibroid resection and endometrial ablation, and include the following rare, but serious events:

- Bradycardia or other cardiovascular response to the procedure
- Thermal damage to adjacent organs or tissue
- Air/gas embolism
- Deep venous thrombosis/pulmonary embolism
- Myocardial infarction
- Hemorrhage
- Pelvic infection, including pelvic inflammatory disease (PID), endometritis, or tuboovarian abscess, fibroid or pelvic abscess
- Sepsis
- Bowel or bladder perforation
- Unintended/inadvertent ablation of undiagnosed endometrial carcinoma/uterine sarcoma, leading to delayed diagnosis and a potentially higher cancer stage at the time of diagnosis

Passage of an ablated myoma per vaginam may occur. Lower severity outcomes are associated with smaller fibroids. Passage of a larger fibroid is more likely to require medical or surgical intervention. The incidence is significantly less common than that observed for UAE. Risks associated with surgical intervention are considered equivalent to those associated with standard therapy.

Retention of a device fragment may occur.

Safety of treatment with the Sonata System with respect to future pregnancies has not been studied. For this reason, patients are not able to participate in this study if they may want to become pregnant in the future.

The following more common but less serious side effects and complications can occur:

- Nausea and/or vomiting

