- Abdominopelvic pain or cramping
- Vaginal bleeding or discharge, including increased volume due to shedding of treated fibroid tissue
- Cervical/vaginal laceration or tear
- Minor infection, including urinary tract infection, vaginal infection, or IV site infection
- Uterine perforation
- Cervical stenosis
- Hematometrium
- Fever
- Thermal burn at the site of the dispersive electrodes
- Allergic reaction to device materials

There are also standard risks associated with the screening assessments, the chosen anesthesia method, magnetic resonance imaging, and with exposure to gadolinium-based contrast agents used in conjunction with the MRI.

A more detailed discussion of risks is provided in the Investigator's Brochure.

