5.6.8.2 Handling of Dropouts or Missing Data

Reduction in MBL at 12 Months

Missing 12-month menstrual blood loss data will be imputed using last observation carried forward (LOCF). Subjects which undergo surgical reintervention to manage fibroid symptoms prior to 12 months will be excluded from the Reduction in Menstrual Blood Loss analysis.

Surgical Reintervention for HMB due to Treatment Failure at 12 Months

Life-Table methods will be used to calculate the success rate and 95% confidence interval for the rate of surgical reintervention during 12 months. Therefore, subjects that are discontinued prior to 12 months for reasons other than surgical reintervention will be considered censored.

Sensitivity Analyses

Sensitivity analyses will also be conducted to examine the impact of missing data. A worst-case analysis (all missing data imputed as failures) and best-case analysis (all missing data imputed as successes) will be performed. In addition, a tipping point analysis will be performed.

Secondary Endpoint Analyses

No imputations will be made for missing secondary endpoint data.

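### Treated women withdrawn under Protocol 10.6 are not followed for later surgical reinterventions or new adverse events, which may modestly overstate the reintervention success rate

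*Protocol*

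**What the plan says.** Protocol 10.6 E is mandatory: "A subject will be withdrawn from the study if, subsequent to enrollment, she is diagnosed with any condition that could affect menstrual bleeding volume". Pregnancy after treatment is the other trigger in that paragraph. No condition caused by the device or procedure is exempted.

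Two further rules are discretionary. Protocol 10.5 A: "Poor subject adherence may result in the sponsor discontinuing the subject from the study". Protocol 10.6, first paragraph: "Subjects may be involuntarily removed from the study for failure to adhere to the protocol, failure to attend follow-up visits". That paragraph also allows removal on safety grounds.

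At exit, 10.6 A and B call for an exit visit where possible and an exit form. Under 10.6 C, "as many of the month 12 study procedures should be performed as possible at the time of withdrawal". After exit, 10.6 D follows adverse device effects that are still ongoing, and 10.6 E asks for pregnancy outcome. Section 14.2 A has adverse events followed until they resolve or are judged chronic or stable, but the duty to look for events covers subjects while they are in the study. Section 14.1 A, Note 3, keeps elective reintervention for heavy bleeding out of the adverse event definition.

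SAP 5.6.8.2 says of the reintervention endpoint that "subjects that are discontinued prior to 12 months for reasons other than surgical reintervention will be considered censored". SAP 5.6.1 removes from the FAS any woman diagnosed with a condition that undermines the bleeding assessment. The FAS is the primary population (SAP 5.6), and the only sensitivity table in the SAP's index, Table 14.2.3.2.3, is for the FAS.

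**The concern.** In a drug trial, withdrawal at least stops exposure. Here the intervention is over on Day 0, so withdrawing a treated woman ends observation and nothing else. An unusable bleeding diary is a reason to treat her differently in the MBL analysis. It is not a reason to stop asking about surgery or safety.

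The trigger in 10.6 E is broad. Protocol 13.1 lists, among other risks, "Cervical stenosis", hematometrium and endometritis, as well as "Unintended/inadvertent ablation of undiagnosed endometrial carcinoma/uterine sarcoma, leading to delayed diagnosis". The protocol does not name these as withdrawal triggers, but the unrestricted wording can cover them. It can also cover an adenomyosis or polyp diagnosis made while continued bleeding is being investigated, and such women may well go on to surgery. An operation after exit would reach neither the co-primary endpoint nor, if elective and for heavy bleeding, the adverse event data.

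At stake are a possible overstatement of one of the two co-primary success rates and a gap in new safety events after exit. Neither can be rebuilt at analysis.

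**Working it through.** **The plan's own figures.** Protocol 19.1 B and SAP Table 4 assume 90% free of reintervention against a threshold of 75%, with 75 women for 90% power. With an exact (Clopper-Pearson) two-sided 95% interval, 64/75 is the smallest passing count, and power at 90% is 93.1%. The figure reproduces. Protocol 19.1 C: 125/(1 - 0.15) = 147.06, hence 147 treated.

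**Margin at 147.** The smallest count with an exact lower confidence limit (LCL) of at least 75% is 121/147 = 82.3% (LCL 75.2%); 120/147 gives 74.4%. So 26 reinterventions pass and 27 fail. The SAP uses life-table methods without naming the interval formula, so the exact binomial serves here as a yardstick for complete follow-up.

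**Assumptions (not in the documents).** 5-10% removed, that is 7 to 15 of 147; 30-40% of them reoperated by month 12; 10% in women who stay, the planning rate.

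**Size of the bias.** Events missed: 7 × 0.30 = 2.1 to 15 × 0.40 = 6.0. Dividing these by 147 does not give the bias, because censoring or exclusion implicitly gives removed women the rate of those who stay. The net bias is (removed/147) × (rate in removed - rate in stayers):

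- low: 7/147 × (0.30 - 0.10) = 1.0 point
- high: 15/147 × (0.40 - 0.10) = 3.1 points

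If the 15 women are all censored event-free at month 6, the life-table estimate is about 90.5%, against a true (132 × 0.90 + 15 × 0.60)/147 = 86.9%. The gap is then 3.6 points, slightly more because their event-free months before exit are credited.

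**Effect on the decision.** The censored LCL uses Greenwood's formula with exit at month 6. The last column counts every woman's events to month 12.

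| Rate in stayers | Removed | Rate in removed | Expected events | Censored LCL | LCL, all followed |
|---|---|---|---|---|---|
| 10% | 7 | 30% | 14.0 + 2.1 ≈ 16 | 85.4% | 82.9% pass |
| 10% | 15 | 40% | 13.2 + 6.0 ≈ 19 | 85.6% | 80.6% pass |
| 10% | 15 | 100% | 13.2 + 15.0 ≈ 28 | 85.6% | 73.7% fail |
| 15% | 15 | 30% | 19.8 + 4.5 ≈ 24 | 79.9% | 76.7% pass |
| 15% | 15 | 40% | 19.8 + 6.0 ≈ 26 | 79.9% | 75.2% pass |
| 15% | 15 | 50% | 19.8 + 7.5 ≈ 27 | 79.9% | 74.4% fail |

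The censored result does not respond to what happens after exit. At the planning rate with 15 removed, reaching 27 events would need 27 - 13.2 = 13.8 of the 15 to be reoperated (92%).

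**Coverage by the sensitivity analyses.** Women removed for adherence stay in the FAS, so the worst-case and tipping-point analyses reach them. Women excluded from the FAS under SAP 5.6.1 are outside the planned sensitivity table.

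**The case against.** Several points on the other side stand.

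- **Safety.** A reader might infer that women with device complications lose safety follow-up. The documents do not support that. A triggering event at least possibly related to the device counts as an adverse device effect (14.1 I). If ongoing at exit, it is followed to six weeks after treatment or until resolved or stable, whichever is later (10.6 D; see also 14.2 A). What is lost is new events.
- **Direction.** A reader might infer that the bias always favours the device. That requires a higher reintervention rate in removed women. It is plausible for diagnoses made during work-up of continued bleeding, but nothing shows it for women removed for adherence or missed visits.
- **Mechanism.** Not all these women are censored. The FAS criterion is close to 10.6 E but narrower, and women who meet it are excluded. Amending the protocol alone would leave their events out of the primary estimate.
- **Endpoint definition.** The co-primary counts surgery for heavy bleeding due to treatment failure. A hysterectomy for cancer or a procedure for hematometrium is not obviously that. Screening for adenomyosis, endometriosis, hyperplasia and larger or multiple polyps also makes such diagnoses less likely.
- **Adherence removals.** These are optional, and Protocol 10.9 requires contact attempts and rescheduling after missed visits. That removal might be steered by known diary scores is conjecture.

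None of this supplies a provision for collecting reinterventions or new adverse events after exit.

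**Conclusion.** The gap in data collection is clear from the text. The bias is conditional: success is overstated only if removed women are reoperated more often than those who stay. Under the stated assumptions it is about 1 to 3 percentage points, or up to 3.6 in the month-6 censoring illustration.

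A reader might infer that study success is in doubt. The figures do not support that. Across the assumed ranges the criterion is still met, even with 15% reintervention among women who stay, though there the upper end (26 events) leaves no margin. The result turns only when the true success rate is near 82.3% and removed women do worse than assumed, as in the 50% row. This is a cheap improvement rather than a threat to the trial's conclusion, worth making because events not collected cannot be recovered.

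**What to change.** **Protocol.** For women already treated, amend 10.5 A, 10.6 A and 10.6 E so that a bleeding-related diagnosis or poor adherence is recorded with its date and may end or invalidate the diary assessment, but does not end follow-up. Adverse events and surgical reintervention continue to be collected, by phone if needed, through 12 months and at the year 2 and 3 contacts. Only withdrawal of consent, loss to follow-up or death ends this. Section 10.6 F, on women not yet treated, can stay as it is. The protocol already separates visits from outcome collection in this way for pregnancy (12.3 B).

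**SAP.** In 5.6.1, apply the FAS exclusion for bleeding-confounding conditions to the MBL endpoint only. In 5.6.4.1 and 5.6.8.2, include all treated women in the reintervention life-table, count events under the existing endpoint definition, and run the sensitivity analyses on the same women.

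**Cost.** A wording amendment to both documents and a few phone contacts. No added subjects or procedures. The reintervention rate may come out slightly less favourable.
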